1.6 Background and Clinical Studies of Tiragolumab

Tiragolumab is a fully human immunoglobulin G1 (IgG1)/kappa mAb derived in Open Monoclonal Technology (OMT) rats that binds T-cell Immunoreceptor with Immunoglobulin and Immunoreceptor Tyrosine-Based Inhibition Motif [ITIM] domains (TIGIT) and prevents its interaction with the poliovirus receptor (PVR). The recombinant antibody is produced in Chinese hamster ovary (CHO) cells and consists of two heavy chains (456 amino acid residues each) and two light chains (220 amino acid residues each).

The inhibitory immunoreceptor TIGIT has been shown to limit the effector function of tumor-associated lymphocytes. TIGIT is an immunoglobulin (Ig) super family member expressed on subsets of activated T cells and natural killer (NK) cells, and found highly expressed in tumor tissue and in tumor-infiltrating immune cells in many human cancers, including, but not limited to NSCLC, breast cancer, multiple myeloma, and non-Hodgkin lymphoma. In multiple tumor types, TIGIT is coordinately expressed with PD-1²¹⁻²³. Genetic ablation or antibody blockade of TIGIT has been shown to enhance NK cell killing, CD4+ and CD8+ T-cell activation, and effector function in vitro and in vivo in nonclinical models.^{21, 22, 24, 25} In the nonclinical tumor models, TIGIT interacted with high affinity to CD155 (also known as PVR), which also has an activating counter-receptor CD226. Activation of TIGIT on T cells and NK cells was demonstrated to limit proliferation, effector cytokine production, and killing of target tumor cells.^{21, 22, 24}

Therapeutic blockade of TIGIT by tiragolumab represents an attractive strategy for cancer therapy and is expected to enhance the magnitude and quality of the tumor-specific T-cell responses, which may result in improved meaningful anti-tumor activity when tiragolumab is used in combination with other cancer immunotherapies and administered with chemotherapy. The available nonclinical and clinical data provide a strong rationale for evaluating the potential clinical benefit of tiragolumab in cancer patients. Refer to the tiragolumab Investigator's Brochure for details on nonclinical studies.

Clinically study GO30103²⁶ is a first-in-human, open-label, multicenter, global, dose-escalation/dose-expansion Phase I study designed to evaluate the safety, tolerability, and pharmacokinetics of tiragolumab as a single agent (Phase Ia) and in combination with

atezolizumab (Phase Ib) in patients with locally advanced, recurrent, or metastatic incurable tumors, including urothelial cancer, renal cell cancer, NSCLC, head and neck squamous cell carcinoma, esophageal cancer, colorectal cancer (CRC), gastric cancer, cholangiocarcinoma, and triple-negative breast cancer.

As of the data cutoff date of 3 December 2018, 42 patients had received tiragolumab monotherapy at doses of 2–1200 mg, and 164 patients had received tiragolumab at doses of 2–600 mg in combination with 1200-mg atezolizumab. The best observed response with tiragolumab monotherapy was prolonged stable disease in 8 of 42 patients, with some patients (including 1 patient with CRC) experiencing a decrease in tumor size. Among 164 patients receiving tiragolumab in combination with atezolizumab, a complete response was observed in 3 patients (including 1 patient with esophageal cancer), a partial response was observed in 22 patients (including patients with esophageal cancer), and stable disease was observed in 38 patients. Among 4 patients with urothelial cancer receiving tiragolumab in combination with atezolizumab, a confirmed partial response was observed in 3 patients.

No maximum tolerated dose, dose-limiting toxicities (DLTs), or clear dose-related trends in the incidence or severity of adverse events have been determined for tiragolumab as a single agent or in combination with atezolizumab. A fatal case of hepatic toxicity culminating in fulminant liver failure occurred in a patient with metastatic head and neck cancer receiving single-agent tiragolumab at the highest dose cleared for enrollment (1200 mg) (see the tiragolumab IB for details). No other fatal cases of fulminant liver failure have been observed.

Overall, tiragolumab as a single agent or in combination with atezolizumab has been well tolerated, adverse events have been manageable, and the safety profile is observed to be consistent across different solid tumor indications.

A second study GO40290²⁷ is a global, multicenter, randomized, blinded, placebo-controlled Phase II study designed to evaluate the safety and efficacy of tiragolumab plus atezolizumab compared with placebo plus atezolizumab in patients with previously untreated, locally advanced unresectable, or metastatic PD-L1-selected NSCLC.

As of the primary clinical cutoff date of 30 June 2019, a total of 135 patients with a PD-L1 TPS \geq 1% were included in the intent-to-treat (ITT) population and were randomly assigned to receive tiragolumab plus atezolizumab (n = 67) or placebo plus atezolizumab (n = 68). Of the enrolled patients, 43.0% of patients had a TPS \geq 50% relative to 57.0% of patients with a TPS 1%–49%, 59.3% had non-squamous histology compared with 40.7% of patients who had squamous histology, and 10.4% of patients were never-smokers versus 89.6% who had smoked. These three stratification factors were well balanced between treatment groups. Demographics were also generally well balanced between treatment groups, with a median age of 68 years in both the tiragolumab plus atezolizumab and placebo plus atezolizumab arms. There were more females (41.8% vs. 29.4%) and more White patients (62.7% vs. 58.8%) in the tiragolumab plus atezolizumab arm compared with the placebo plus atezolizumab arm.

In the ITT population, the confirmed ORR was higher in the tiragolumab plus atezolizumab arm (31.3%) than in the placebo plus atezolizumab arm (16.2%). In the subgroup of patients with TPS \geq 50%, the confirmed ORR was higher in the tiragolumab plus atezolizumab arm (n = 29; 55.2% [95% CI: 35.4%, 75.0%]) than the placebo plus atezolizumab arm (n = 29; 17.2% [95% CI: 1.8%, 32.7%]). Of note, responders in the tiragolumab plus atezolizumab arm included patients with both squamous and non-squamous histology.

In the ITT population, investigator-assessed PFS was improved in the tiragolumab plus atezolizumab group over the placebo plus atezolizumab group (stratified HR = 0.57 [95% CI: 0.37, 0.90]; median PFS 5.4 vs. 3.6 months, respectively). In the subgroup of patients with TPS \geq 50%, investigator-assessed PFS was improved in the tiragolumab plus atezolizumab group over the placebo plus atezolizumab group (unstratified HR = 0.33 [95% CI: 0.15, 0.72]; median PFS not estimable (NE) vs. 3.9 months, respectively) (Roche unpublished data on file).

1.7 Rationale for this Study

Based on the results of the ABACUS, PURE-01, CITYSCAPE trials and our unpublished data on clinical outcomes from the initial monotherapy treatment cohort, it appears that there is significant clinical activity of both of these agents, including indications of potential synergy, with acceptable risks. Given the need for novel therapies to improve outcomes for patients with MIBC ineligible for cisplatin-based chemotherapy, this study offers a potentially therapeutic option. It will additionally provide a wealth of correlative biologic and immunologic data to better understand the mechanism(s) by which these therapies work and identify prognostic and predictive biomarkers.

1.8 Rationale for the Study Design

This study will evaluate the pathologic and immunologic changes induced by atezolizumab-based therapy in bladder tissues compared to pretreatment biopsies. This study has two cohorts (Cohort A and Cohort B) and will accrue each cohort sequentially (i.e., Cohort A will fully accrue, then Cohort B).

Cohort A: Atezolizumab Monotherapy

In the initial monotherapy multi-dose phase (Cohort A), the effects of increasing numbers of doses of atezolizumab will be explored. Similarly, the safety, feasibility, and efficacy of administering up to 3 doses of atezolizumab in patients scheduled for cystectomy will also be examined.

- Multi-dose phase (fully accrued as of October 2020): A fixed number of 6 patients will be accrued at each dose level in the multi-dose portion of the study to allow for investigation into the immunologic impact of different cumulative doses of atezolizumab prior to cystectomy. It is unknown whether multiple doses of atezolizumab are necessary to achieve a complete response or a durable remission as opposed to a single dose, and accrual of 6 patients at each dose level will allow for a preliminary estimate of the efficacy of each cumulative dose level. The safety profile of atezolizumab is well established from multiple Phase I - III studies, and treatment related Grade 3 or 4 toxicities were rare. The multi- dose portion may better inform future studies of neoadjuvant atezolizumab and potentially allow for shorter neoadjuvant courses to be administered.
- Cohort A expansion phase opened after the multi-dose portion of Cohort A completed, consisting of up to 27 total patients in Cohort A. In order to reduce the number of subjects needed for this study and allow for faster study completion, the 6 subjects treated at the highest dose from the multi-dose phase of the study will be included as part of the expansion cohorts, therefore the total accrual to the expansion cohort after the multi-dose portion of Cohort A will be up to 9 subjects. The highest dose level is chosen for the expansion cohorts as it is expected that administration of multiple doses of atezolizumab will best enhance immune responses and lead to better clinical responses. These expansion cohorts will allow for a better estimate that treatment-related grade 3 or 4 events, or delays in cystectomy >12 weeks, are observed at a frequency of less than <33%. It will also allow for an exploratory estimation of efficacy of atezolizumab in this setting, and for further characterization of the immunologic effects of atezolizumab in this patient population.

Cohort B: Atezolizumab + Tiragolumab

After completion of enrollment into Cohort A, and upon approval of Amendment 4.3 (October 19, 2020) the study will begin accrual into Cohort B, where participants will receive combination neoadjuvant therapy with atezolizumab (1200mg IV on Day 1 of a 21 day cycle) and tiragolumab (600mg IV on Day 1 of a 21 day cycle) as neoadjuvant treatment for an intended total of three treatment cycles prior to an intended radical cystectomy. Similar to Cohort A, the safety and efficacy of administering up to 3 doses of atezolizumab in combination with tiragolumab preoperatively in patients scheduled for cystectomy will be examined. No adjuvant therapy will be offered as no study to date has shown benefit for adjuvant PD-1 therapy in urothelial cancer patients who had received prior immunotherapy.²⁸ Recently Checkmate-274 study had a press release indicating a DFS benefit for nivolumab over placebo for high-risk patients with urothelial cancer following radical cystectomy however none of these patients have had prior neoadjuvant immunotherapy.

- Safety Lead-in: As adding tiragolumab together with atezolizumab in patients with NSCLC generates only minimal additive toxicity, this study will start with an initial safety lead-in of 6 patients at which time enrollment will pause to assess the safety of this combination treatment. If dose limiting toxicities are met (certain AEs or surgery delay, as defined in Section 5.4) then fewer doses of tiragolumab will be evaluated (See **Cohort B Safety Lead-in Schema**).

- Expansion: Once the intended treatment regimen is established following completion of the safety assessment, an additional 15 patients will be enrolled at the same regimen for a total of 21 patients on that treatment regimen.

1.9 Correlative Studies

In addition to evaluating the change in immunologic infiltration in tumor tissues induced by study therapy, the safety, toxicity, and efficacy of neoadjuvant atezolizumab-based therapy, this study aims to more thoroughly characterize the immunologic response induced by treatment with study therapy.

More specifically, bladder tissue taken at the time of surgery and peripheral blood will be analyzed immunohistochemically and genetically in order to:

1. Characterize the tumor and immune cell subsets
2. Explore the location of tumor infiltration lymphocytes (e.g. within tumors, at tumor periphery)
3. Characterize T cell receptor diversity
4. Explore the correlation of tumor PD-L1 expression across different grades and stages of disease with response to therapy.

In addition, serum and blood will be analyzed to determine whether antigen-specific immune responses are modulated and to quantify and characterize circulating immune cell subsets.

2 Study Objectives

2.1 Primary Objectives and Endpoints

Cohort A (Atezolizumab monotherapy):

1. Multi-dose cohorts: To assess the intratumoral immune response associated with increasing numbers of Atezolizumab treatments.
 - Endpoint: CD3+ T cell count/ μm^2 between the pretreatment biopsy and the cystectomy tissue following single and multiple neoadjuvant Atezolizumab infusions.
2. Expansion cohort: To assess the anti-tumor activity of Atezolizumab as determined by the pathologic T0 rate (pT0N0) at the time of cystectomy.
 - Endpoint: Pathologic T0 rate at the time of cystectomy, defined as the pathologic absence of disease in the bladder after resection (See section 7.1.1).

Cohort B (Atezolizumab + tiragolumab)

1. To assess the safety of neoadjuvant combination treatment with atezolizumab and tiragolumab according to CTCAE v5.0 in a curative intent treatment population of urothelial carcinoma patients undergoing radical cystectomy.
 - Endpoint: The percentage of patients in Cohort B with treatment-related adverse events according to CTCAE v5.0 or treatment-related delays in surgery beyond 12 weeks following administration of neoadjuvant treatment with atezolizumab and tiragolumab.
2. To assess the anti-tumor activity of Atezolizumab + Tiragolumab as determined by the pathologic T0 rate (pT0N0) at the time of cystectomy.
 - Endpoint: Pathologic T0 rate at the time of cystectomy, defined as the pathologic absence of disease in the bladder after resection (See section 7.1.1).

2.2 Secondary Objective(s) and Endpoint(s)

Cohorts A and B

Multi-Dose Cohorts

1. To evaluate the safety and feasibility of administering up to 3 cycles of Atezolizumab pre-operatively to patients with resectable urothelial bladder cancer. Note this is the coprimary objective for Cohort B.
 - Endpoint: The percentage of patients with treatment-related adverse events according to CTCAE v5.0 or treatment-related delays in surgery beyond 12 weeks following administration of neoadjuvant treatment with atezolizumab with or without tiragolumab. Note for Cohort A CTCAE v4.0 was used.

Expansion Cohorts

1. To assess the anti-tumor activity of neoadjuvant treatment as determined by pathologic partial response (<pT2N0) assessed at the time of radical cystectomy
 - Endpoint: Percentage of patients with pathologic downstaging (<pT2N0) at the time of radical cystectomy
2. To determine the 2-year relapse-free survival (RFS) rate and median RFS from time of radical cystectomy in patients treated with neoadjuvant therapy
 - Endpoint: 2-year RFS rate and median RFS in ITT population
3. To determine the 2-year overall survival (OS) and median OS from time of radical cystectomy in patients treated with neoadjuvant therapy
 - Endpoint: 2-year OS rate and median OS in ITT population
4. To assess the intratumoral immune response of neoadjuvant by comparing pre-treatment TURBT with post-treatment cystectomy tumor specimens

- Endpoint: Association of tumor and T-cell PD-L1/PD-1 immunohistochemical expression with disease response

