8.3.2 Analysis of Primary Endpoints

The immunologic effect of activity study therapy within bladder tissue will be measured by a change in the CD3⁺ T cell count/ μm^2 between the pretreatment biopsy and the cystectomy tissue following study therapy administrations. Immunohistochemistry will be performed in the [name] lab at UCSF per established SOPs. Based on prior experience tissue will be designated into 3 distinct compartments: benign epithelium, tumor centers, and tumor interfaces. Tumor interfaces will be defined as fields where malignant and benign epithelium are present. Automatic cell counts for single- and double-stained cells will be determined for each field with color-specific algorithms.

The cell count for each compartment will be reported as the mean for each of the five quantitated fields. Cells of interest will include CD3⁺ T cells, CD3⁺ Ki67⁺ proliferative T cells,

CD4+ FoxP3- helper T cells, CD4+ FoxP3+ regulatory T cells, CD8+ cytotoxic T cells, as well as PD-1 expression on the different lymphocytes. In collaboration with Genentech, PD-L1 expression on both tumor and immune cells within the microenvironment will be assessed.

For each cohort, the change of T cell counts from pre-treatment to post-treatment will be calculated for each compartment as log2 of the ratio of post-treatment vs. pre-treatment counts. If different regimens are used (for example atezolizumab x 3 doses and tiragolumab x 2 doses) two-sample Wilcoxon rank sum test will be used to compare the difference of the change from pretreatment to post-treatment between cohorts to assess if the intratumoral immune response associated with increasing numbers of treatments. No multiple comparison adjustments will be performed.

8.3.2.1 pT0 rate

Point estimates and 95% confidence intervals of pathologic T0 rate at the time of cystectomy as defined in Section 7.1.1 will be obtained for subjects treated with atezolizumab and tiragolumab. Pathologic T0 rate at the time of cystectomy will be compared with the null hypothesis rate (see Section 8.1) separately by using one-sample proportion test.

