8.3.3.2 PD-1/PD-L1 expression and response

For each dose level as well as for each individual expansion cohort, Fisher's exact test will be used to test the association of baseline tumor and T-cell PD-L1/PD-1 immunohistochemical expression with disease response.

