8.3.4.2 Tissue immune subset quantification and localization

For all subjects, immune cell subsets and localization will be summarized by changes from baseline to after treatment using descriptive statistics.

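### Secondary objective 4 asks for a pre/post tissue comparison, but its endpoint is PD-L1/PD-1 expression versus response, and no within-cohort pre/post test is specified for the tissue IHC measures

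*Combined protocol and SAP*

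**What the plan says.** Section 2.2, Expansion Cohorts, item 4, sets the objective: "To assess the intratumoral immune response of neoadjuvant by comparing pre-treatment TURBT with post-treatment cystectomy tumor specimens". The single endpoint listed under it is "Association of tumor and T-cell PD-L1/PD-1 immunohistochemical expression with disease response". That endpoint names no timepoint and no change measure.

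The matching analysis, section 8.3.3.2, applies to each dose level and each expansion cohort: "Fisher's exact test will be used to test the association of baseline tumor and T-cell PD-L1/PD-1 immunohistochemical expression with disease response". The restriction to baseline appears here, not in the endpoint text.

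Four other places bear on the pre/post question:

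- Section 8.3.2: "the change of T cell counts from pre-treatment to post-treatment will be calculated for each compartment as log2 of the ratio". The test on that quantity is conditional on different regimens being used, and then a "two-sample Wilcoxon rank sum test will be used to compare the difference of the change from pretreatment to post-treatment between cohorts".
- Section 8.3.4.2 (exploratory): tissue immune subsets "will be summarized by changes from baseline to after treatment using descriptive statistics".
- Section 8.3.4.1 (exploratory): PD-L1 is scored 0 to 3 on pre-treatment and cystectomy tissue, and the scores feed the relationship with clinical response. No pre/post PD-L1 comparison is given.
- Sections 8.3.4.3, 8.3.4.5 and 8.3.5.1 (exploratory): paired tests of immune gene expression, tumour gene copy number and circulating immune cells.

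**The concern.** The objective concerns change within a patient: did treatment alter the immune infiltrate between TURBT and cystectomy? The endpoint concerns prediction: do patients with a given expression level respond more often? A clear answer to the second says nothing about the first. With expression taken at baseline, the only post-treatment information in the Fisher table is response status, so no post-treatment immune measurement is used.

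At stake is whether a named secondary objective can be answered by the endpoint assigned to it, in either expansion cohort. Followed literally, the plan gives objective 4 a baseline-biomarker result. The T-cell change that would answer it is calculated elsewhere, without a within-cohort test or interval.

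**Working it through.** **Step 1. Match the objective to the analyses.**

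| Section | Measure | Uses post-treatment tissue immune data? | Within-cohort pre/post test? |
|---|---|---|---|
| 2.2 item 4, objective | TURBT versus cystectomy tissue | required | implied |
| 2.2 item 4, endpoint | PD-L1/PD-1 versus response | timepoint not stated | no |
| 8.3.3.2 | baseline PD-L1/PD-1 versus response, Fisher | no | no |
| 8.3.2 | log2(post/pre) T-cell count | yes | no; rank-sum between cohorts only |
| 8.3.4.1 | PD-L1 score at both times, linked to response | yes | no |
| 8.3.4.2 | immune subsets | yes | no; descriptive |
| 8.3.4.3 | immune gene expression | yes | yes, paired t (exploratory) |
| 8.3.4.5 | tumour gene copy number | tumour DNA, not an immune measure | yes, paired Wilcoxon (exploratory) |
| 8.3.5.1 | circulating immune cells | blood | yes, paired Wilcoxon (exploratory) |

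No row combines a tissue IHC measure with a within-cohort pre/post test, and none of the three paired tests is assigned to objective 4.

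**Step 2. The plan's own figure.** Section 8.1 gives no sample size or power for objective 4. The nearest figure is Cohort B's 21 patients for pT0 of 30% versus 60%, at 0.05 and 80% power. With the arcsine effect size:

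- h = 2·arcsin(√0.60) − 2·arcsin(√0.30) = 0.613
- n = ((1.960 + 0.842) / 0.613)² = 20.9, so 21 (two-sided 0.05)

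The figure reproduces. It sets the number of patients available for a pre/post analysis but was not chosen for one.

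**Step 3. What a within-cohort test could detect.** Assumptions: mean log2 ratio 1 (a 2-fold rise), two-sided 0.05, one-sample t-test as a stand-in for the signed-rank test. The 2-fold rise and SD 1 are borrowed from section 8.1, where they plan a comparison between Cohort A dose levels. That section does not say the SD is on the log2 scale. SD 1.5 and 2 are added to show the range.

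Power comes from the non-central t distribution with n − 1 degrees of freedom and non-centrality √n · (1/SD). For n = 21 and SD 1.5 the non-centrality is 4.583/1.5 = 3.06 against a critical value of 2.086, giving 83%.

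How many pairs there are depends on residual tumour. If a pT0 bladder gives no tumour compartment to count (assumption), the pairs left are:

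- at 30% pT0: 21 × 0.70 = 14.7, about 15
- at 60% pT0: 21 × 0.40 = 8.4, about 8

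| Pairs | SD 1 | SD 1.5 | SD 2 | Change detectable with 80% power |
|---|---|---|---|---|
| 21 | 99% | 83% | 59% | 0.64 SD |
| 15 | 95% | 67% | 44% | 0.78 SD |
| 8 | 68% | 37% | 23% | 1.16 SD |

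Fifteen is also the maximum size of the Cohort A expansion group, so that row applies to Cohort A if every patient gives a pair. Simulated signed-rank power at a change of 1 SD agrees to within about 6 points: 0.99, 0.94 and 0.62 for 21, 15 and 8 pairs.

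**The case against.** Four counter-arguments carry weight.

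- **The plan is not without pre/post tests.** A reader might infer that a single-regimen Cohort B has none. The documents do not support that. Section 8.3.4.3 has a paired t-test of immune gene expression between pre-treatment and cystectomy samples with no condition on regimen, and sections 8.3.4.5 and 8.3.5.1 add further paired tests. The gap is confined to the IHC measures.
- **Cystectomy tissue is not absent from the analysis.** A reader of section 8.3.3.2 alone might conclude that it is. Response is itself determined from the cystectomy specimen (section 7.1.1), and section 8.3.4.1 scores PD-L1 on cystectomy tissue and links that scoring to response. What follows is that 8.3.3.2 and 8.3.4.1 disagree, or are unclear, on the timepoint.
- **The rank-sum test can be read as covering Cohort A versus Cohort B.** These are different regimens, and exploratory objective 2 plans that comparison. Cohort B could therefore enter a formal test even if it stays on its starting regimen. This stands, but the test compares two changes. It cannot show whether infiltration changed within Cohort B.
- **A small phase II cohort may properly describe a biomarker change without testing it.** This is the strongest point. Description would be acceptable had it been assigned to objective 4. Instead, section 2.2 assigns a different question, and the descriptive summary sits among the exploratory analyses.

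One might also infer that the Fisher result will be published as evidence of an intratumoral immune response. Nothing in the plan says so, and section 8.3.3.2 is titled for what it does.

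**Conclusion.** The concern holds in a limited form. Objective 4 and its endpoint ask different questions, and section 8.3.3.2 settles on the one the objective does not pose. For the tissue IHC measures no within-cohort pre/post test is specified in either expansion cohort. That conclusion rests on the text alone and needs no numerical assumption.

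The power figures only show what a repair could deliver. In Cohort B they run from 99% (21 pairs, SD 1) to 23% (8 pairs, SD 2) for a 2-fold change. They depend on the assumed log2 SD and on whether pT0 bladders give a usable pair. Neither the sample size, the safety stopping rule nor the pT0 conclusion depends on this point. It should be corrected before analysis because a secondary objective is otherwise left unanswered by its own endpoint.

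**What to change.** 1. In section 2.2, make the log2 post/pre CD3+ ratio from section 8.3.2 the endpoint of secondary objective 4.
2. In section 8.3.3, report it within each expansion cohort with a Wilcoxon signed-rank test against zero, a Hodges-Lehmann estimate and a 95% interval.
3. State the number of evaluable pairs and how cystectomies without residual tumour are handled. One option is to report the tumour-centre result as conditional on residual tumour, with a sensitivity analysis in a compartment available in all patients. Benign epithelium is a candidate if both specimens contain it.
4. Keep baseline PD-L1/PD-1 versus response as a separately named predictive-biomarker endpoint, and reconcile sections 8.3.3.2 and 8.3.4.1 on the timepoint.

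The cost is wording: the specimens, staining and ratios are already planned. There are three downsides. It adds one more unadjusted secondary test. Precision is limited if many patients are pT0. A tumour-centre analysis restricted to evaluable pairs may drop complete responders, so it would describe mainly patients with residual disease and must be labelled as such.
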